3.3.3 Visit Window

Time windows will be defined for any presentations that summarise values by visit. The following conventions will apply:

- Study day references the date of first dose of study intervention as Day 1.
- The time windows will be exhaustive so that data recorded at any timepoint have the potential to be summarised. Inclusion within the time window will be based on the actual date and not the intended date of the visit.
- The window for visits following baseline is constructed in such a way that the upper limit of the interval falls halfway between the two visits (the lower limit of the first post-baseline visit is Day 2). If an even number of days exists between two consecutive visits, then the upper limit is taken as the midpoint value minus 1 day.
- For summaries showing the maximum or minimum values, the maximum/minimum value recorded on treatment during the randomised period

and the on-selumetinib period (as defined in Section 3.3.2.3) will be used (regardless of where it falls in an interval).

- Listings display all values contributing to a timepoint for a patient.
- For visit-based summaries/analyses, if there is more than one value per patient within a time window, then the closest value to the scheduled visit date will be summarised or the earlier, in the event the values are equidistant from the nominal visit date. The listings will highlight the value for the patient that contributed to the summary table, wherever feasible.

Note: In summaries of extreme values, all post-baseline values collected are used, including those collected at unscheduled visits regardless of whether the value is closest to the scheduled visit date.

Note: For the purpose of the visit-based summaries of efficacy data (except tumour volumes and response), the EOT visit will be mapped into one of the planned visit windows. For visit-based safety summaries and for tumour volume and response summaries, the EOT and/or Safety Follow-up Visit will be summarised apart.

3.3.4 Handling of Unscheduled Visits

Unscheduled visits are included in the method of assigning data to scheduled visits described in Section 3.3.3. Unscheduled visits are not included as separate visits in the summary tables.

For summaries at the patient level, such as those of extreme values, all post-baseline values collected are used to derive a patient level statistic including those collected at unscheduled visits and regardless of whether they appear in the corresponding visit-based summary.

3.3.5 Missing Data

In general, other than for partial dates, missing data will not be imputed and will be treated as missing unless specifically described in an analysis section. However, safety assessment values of the form of “ $< x$ ” (i.e., below the lower limit of quantification) or $> x$ (i.e., above the upper limit of quantification) will be imputed as “ x ” in the calculation of summary statistics but displayed as “ $< x$ ” or “ $> x$ ” in the listings.

3.3.5.1 Missing AE or Concomitant Medication Dates

For missing AE/concomitant medication dates, the imputation of dates for AEs and concomitant medications is performed to determine if an AE is treatment emergent and whether a medication is concomitant. Flags are retained in the database indicating where any programmatic imputation has been applied, and in such cases, any durations are not calculated.

For missing AE/concomitant medication start dates, the following will be applied:

- Missing day: Impute the 1st of the month unless the month is the same as month of the first dose of study drug and the end date is on or after the first dose of study drug or ongoing, then impute first dose date.
- Missing day and month: Impute 1st January unless year is the same as first dose date and the end date is on or after the first dose of study drug or ongoing, then impute first dose date.
- Completely missing: Impute first dose date unless the end date suggests it started prior to this, in which case impute 01 January of the same year as the end date.

An imputed start date of an AE/concomitant medication must be prior to the end date of the AE.

For missing AE/concomitant medication end dates, the following will be applied:

- Missing day: Impute the last day of the month unless the month is same as month of last dose of study drug, then impute last dose date.
- Missing day and month: Impute 31 December unless the year is the same as last dose date, then impute last dose date.
- Completely Missing: Assume that AE/concomitant medication is still ongoing (ie, do not impute a date).

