It is estimated that approximately 212 adult patients will be enrolled at approximately 46 sites across 13 countries to achieve approximately 146 patients randomised to study intervention. Patients will be randomised 1:1 to receive selumetinib or placebo (i.e. 73 patients per arm). Randomisation will be stratified at the central level by average baseline PAin INTensity Scale for Plexiform Neurofibroma (PAINS-pNF) chronic target PN pain score (< 3 and \geq 3) and geographical region (Europe, China, Japan, and Rest of World). A blocked randomisation will be generated, and randomisation will be balanced within the IRT at the central level. The number of patients randomised will be capped at approximately 106 patients with an average baseline PAINS-pNF chronic target PN pain score \geq 3 and approximately 40 patients with an average baseline PAINS-pNF chronic target PN pain score < 3. Patients randomised to selumetinib will receive selumetinib 25 mg/m² orally twice daily (bid) (based on body surface area [BSA], capped at 50 mg bid when BSA is \geq 1.9 m²) in 28-day cycles until a selumetinib discontinuation criterion is met. Patients randomised to placebo will receive placebo orally bid and will receive selumetinib treatment after the end of Cycle 12. Selumetinib capsules will be administered using BSA-based dosing. If it is anticipated that 20% or more of patients (across blinded study intervention groups) withdraw prior to the end of Cycle 16 for reasons other than progression, then recruitment rates notwithstanding, enrolment will continue to randomise at least 50% of the total number of dropout patients to ensure that the primary endpoint is adequately powered.

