3.3.2.4 Treatment-emergent Periods

The analysis of treatment-emergent adverse events (TEAEs) and concomitant medication will be performed separately for TEAEs occurring/concomitant medication taken during the safety randomised period and TEAEs occurring/concomitant medication taken during the on-selumetinib period. While the analysis of TEAEs in the safety randomised period will be comparative of the two treatment groups, TEAEs presented for the on-selumetinib period will be not comparative due to the different exposure periods. To note, the two safety analysis periods are not mutually exclusive.

TEAEs and Concomitant Medication during the Safety Randomised Period

For patients receiving any selumetinib in the safety randomised period, an adverse event (AE) or a concomitant medication is considered treatment emergent during the safety randomised period if the start date/time of the event or worsening date/time (only for AEs) occurs between the date of first dose of study intervention (Cycle 1 Day 1) and last dose of Cycle 12 or date of study intervention discontinuation (end of treatment [EOT]) + 30 days or DCO date, whichever comes first.

For patients receiving placebo in the safety randomised period, an AE or a concomitant medication is considered treatment emergent during the safety randomised period if the start date/time of the event, or worsening date/time of an AE occurs between the date of first dose of placebo (Cycle 1 Day 1) and the crossover date or date of early placebo discontinuation + 30 days or DCO, whichever comes first.

A worsening is defined as having any on-treatment severity during the safety randomised period worse than the baseline severity. The reported severity of an AE that is treatment emergent during the safety randomised period is given by the maximum Common

Terminology Criteria for Adverse Events (CTCAE) grade recorded any time on-treatment during the safety randomised period. The reported outcome of an AE will be the last outcome corresponding to the maximum CTCAE grade recorded on-treatment in the safety randomised period. Seriousness and causality during the randomised period will also be reported as the worst value recorded in the safety randomised period.

TEAEs and Concomitant Medication during the On-Selumetinib Period

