An AE or a concomitant medication is considered treatment-emergent during the on-selumetinib period if the start date/time of the event, or worsening date/time of a AE occurs between the first dose of selumetinib (which will be Cycle 1 Day 1 for patients receiving selumetinib in the safety randomised period and the date of the crossover for patients receiving placebo in the safety randomised period) until 30 days after the last dose of selumetinib or up to DCO, whichever comes first.

A worsening is defined as having any on-treatment severity during the on-selumetinib period worse than the severity of the safety randomised period. Worsening in the on-selumetinib period will be assessed by comparing to the last-recorded value in the safety randomised period.

For AEs of placebo patients starting during the safety randomised period and worsening during the On-Selumetinib period, the stop date of the event during the safety randomised period will be one day prior to the date of the first worsening after crossing over, while the start date of the event during the on-selumetinib period will be equal to the date of first worsening after crossing over.

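### Partial start dates are imputed only against the first dose of study drug, so for placebo participants who cross over, three kinds of partly dated or undated record default to the placebo period even when onset was on selumetinib

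*SAP*

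**What the plan says.** SAP Section 3.3.5.1 states that date imputation "is performed to determine if an AE is treatment emergent and whether a medication is concomitant". It gives three start-date rules:

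- Day missing: "Impute the 1st of the month unless the month is the same as month of the first dose of study drug". In that month the first dose date is used, provided the event ends on or after first dose or is ongoing.
- Day and month missing: "Impute 1st January unless year is the same as first dose date". In that year the first dose date is used, under the same proviso.
- No date: "Completely missing: Impute first dose date unless the end date suggests it started prior to this".

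The one further constraint is "An imputed start date of an AE/concomitant medication must be prior to the end date of the AE". Flags mark every imputed date. Nothing in the section refers to crossover or to the first selumetinib dose.

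SAP Section 3.3.2.4 assigns events to periods. For the placebo arm, an event is treatment-emergent in the randomised period if onset or worsening "occurs between the date of first dose of placebo (Cycle 1 Day 1) and the crossover date" (or early placebo discontinuation plus 30 days, or the data cut-off, if sooner). The on-selumetinib window opens, for these participants, on "the date of the crossover for patients receiving placebo in the safety randomised period". According to SAP Section 1.1, placebo participants "will receive selumetinib treatment after the end of Cycle 12".

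**The concern.** A placebo participant who crosses over has two treatment starts, but the imputation rule knows only the first. Its exception at first dose keeps an event of uncertain date from being placed before treatment. There is no matching exception at the start of selumetinib. Elsewhere the SAP does keep the two anchors apart: Section 3.3.1 gives the on-selumetinib safety set its own baseline, and Section 3.3.2.3 starts the on-selumetinib period at the first selumetinib dose.

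What is at stake is where an event that began on selumetinib is reported. If its date is imputed before crossover, it is counted as a placebo event in the randomised-period tables and is missing from the on-selumetinib tables. The exposure-adjusted rate in Section 4.6.2.2 is affected twice. The participant leaves the numerator, and the denominator then takes the longer exposure time of someone without the event.

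**Working it through.** The plan gives no figure to reproduce, so the check applies the three rules literally.

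**Inputs.** Cycles last 28 days and crossover follows Cycle 12 (SAP Section 1.1), so planned crossover is first dose + 12 × 28 = 336 days. The imputation rules come from SAP Section 3.3.5.1 and the period windows from Section 3.3.2.4. Assumptions: month means calendar month and year, the first dose of study drug is the first dose of randomised treatment, and events are ongoing or end after first dose.

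**One participant.** First dose 15 March 2022, crossover 14 February 2023.

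| Recorded start | Imputed start | Period |
|---|---|---|
| February 2023, no day | 1 February 2023 | placebo |
| March 2023, no day | 1 March 2023 | on-selumetinib |
| 2023, no day or month | 1 January 2023 | placebo |
| 2024, no day or month | 1 January 2024 | on-selumetinib |
| nothing recorded | 15 March 2022 | placebo |

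**All first-dose days in 2022.** True onset is placed on each of the 336 days from crossover, giving 365 × 336 = 122,640 post-crossover onsets. The table shows how many are imputed to a date before crossover.

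| Missing part | Where onset falls | Moved to placebo |
|---|---|---|
| day | crossover month | 5,373 / 5,738 = 93.6% |
| day | later month | 0 / 116,902 = 0% |
| day and month | crossover year | 66,024 / 66,360 = 99.5% |
| day and month | later year | 0 / 56,280 = 0% |
| whole date | any | 122,640 / 122,640 = 100% |

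The exceptions are explained exactly. The 5,738 − 5,373 = 365 unmoved missing-day onsets belong to crossovers on the 1st of a month. The 66,360 − 66,024 = 336 unmoved onsets with day and month missing belong to the crossover on 1 January. In both cases the imputed date equals the crossover date.

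Over all 336 days after crossover, the share moved is 5,373 / 122,640 = 4.4% with only the day missing, 66,024 / 122,640 = 53.8% with day and month missing, and 100% with no date.

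**The opposite error.** Take a 30-day month with crossover day and onset day independent and uniform. The chance that onset preceded crossover is 29 / (2 × 30) = 48%. So about half of the missing-day events in the crossover month really did begin on placebo, and the present rule places those correctly.

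**The case against.** The strongest reply is that very little is affected. The rule touches only the placebo arm, planned at 73 participants. The missing-day rule acts in one calendar month per participant, and dates are queried. The two safety periods overlap, so an event that worsens after crossover is counted on selumetinib as well (Sections 3.3.2.4 and 4.6.2.1). Participants randomised to selumetinib keep all their events in the on-selumetinib tables. Laboratory, vital-sign and echocardiogram summaries do not depend on adverse-event dates. No primary or key secondary inference is involved. All of this stands and limits the size. It does not remove the misassignment, because an undated event that never worsens is lost from the on-drug counts.

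A second reply is that anchoring on the first selumetinib dose exchanges one directional error for another. That is true, and it is a cost of the fix.

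Three stronger readings are tempting, and the documents do not support them:

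- That every partly dated event in or after the crossover month is moved back. Missing-day events in later months, and events with day and month missing in later years, stay on-selumetinib.
- That the randomised comparison is shown to favour selumetinib. In the selumetinib arm, a missing-day event just after Cycle 12 can also be pulled back into the randomised period, so both columns can gain events and the net effect is not determined. The on-selumetinib tables are themselves described as non-comparative.
- That concomitant-medication status is wrong in the same way. Section 4.1.8.1 sets that status by stop date, so only the assignment to a period is affected.

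**Conclusion.** The point holds for three kinds of record from placebo participants who cross over: day missing in the crossover month, unless crossover was on the 1st; day and month missing in the crossover year, unless crossover was on 1 January; and start date completely missing. Followed as written, the rules put these in the placebo randomised period whatever the true onset, and no other section supplies a crossover rule.

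The direction is firm in one respect: events that began on selumetinib are credited to placebo and omitted from on-drug counts and rates. The size is not known. The documents give no number of partial dates, and it is probably small after querying. This is a minor correction to descriptive safety tables. The percentages are conditional on a record being of the stated kind and assume crossover at day 336. Early crossover after progression would change them slightly but not the mechanism.

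**What to change.** Add to SAP Section 3.3.5.1 a rule for participants who crossed over. It applies if the known date parts and the end date allow onset on or after the first selumetinib dose, and one of these is true: the day is missing and the reported month is that of the first selumetinib dose; day and month are missing and the reported year is that of the first selumetinib dose; or the start date is completely missing. In those cases, impute the first selumetinib dose date and count the event only in the on-selumetinib period. The last clause is needed because the crossover date closes one window and opens the other, so an event imputed to that date could otherwise be counted in both. Apply the same dates to the period assignment of concomitant medication.

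The cost is one SAP rule and a small change to the derivation. The downside should be stated beside it. Some events that began on placebo will be counted on drug, including up to about half of crossover-month events with a missing day, and any completely undated placebo-period event whose end date does not rule out later onset. That is the conservative direction, and it extends the convention already used at first dose. The imputation flags already kept allow these records to be identified.

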3.3.5.2 Missing Dates of Diagnosis

For missing dates of diagnosis, if the day and/or month are missing use 01 and/or January. If the year is missing, put the complete date to missing.

3.3.5.3 Missing Death Dates

If a patient is known to have died where only a partial death date is available, then the date of death will be imputed as the latest of the last date known to be alive + 1 from the database and the death date using the available information provided:

- For missing day only: Use the 1st of the month.
- For missing day and month: Use 01 January.

Note: The last date known to be alive for each individual patient is defined as the latest date among all start/end/assessments/collections dates unrelated to death.

3.3.5.4 AEs With Missing Causality

AEs that have missing causality (after data querying) will be assumed to be related to study drug.

3.3.6 COVID-19 Impact

Summaries of data relating to the impact of the global/country COVID-19 situation will be generated, including the following:

- Discontinuations of study intervention and withdrawal from study due to global/country situation
- Important protocol deviations (IPDs) related to the global/country situation
- Global/country situation study disruptions
- Listing for patients affected by the global/country situation
- Listing for patients with reported issues in the Clinical Trial Management System due to the global/country situation

3.3.7 Multiplicity/Multiple Comparisons

The MTP will define which significance levels should be applied to the interpretation of the raw p-values for the primary endpoint (ORR by the end of Cycle 16), 1st key secondary endpoint (change from baseline in PAINS-pNF chronic target PN pain intensity score at Cycle 12), and 2nd key secondary endpoint (change from baseline in PlexiQoL total score at Cycle 12) intended for label claims and is described in [Figure 2](#).

Significance levels will be adjusted for each confirmatory endpoint in order to preserve the overall type 1 error (familywise error rate) at 5% (two-sided) in the strong sense by defining a gatekeeping strategy where the families of hypotheses are tested in a sequential manner. Each family will be defined by one endpoint and the two associated tests (DCO1 and DCO2): the first family based on the primary endpoint, the second family based on the 1st key secondary endpoint, and the third family based on the 2nd key secondary endpoint.

Full alpha of 0.05 (two-sided) will be initially assigned to the primary endpoint. If statistical significance for the primary endpoint is reached (either at DCO1 or at DCO2), the overall alpha of 0.05 (two-sided) will be sequentially re-assigned to test the 1st key secondary endpoint. If statistical significance is reached for the 1st key secondary endpoint, then the overall alpha of 0.05 (two-sided) will be sequentially re-assigned to test the 2nd key secondary endpoint. If statistically significance is not reached for the primary endpoint, the p-value of the key secondary endpoints will only be nominal. If statistical significance is not reached for the 1st key secondary endpoint either at DCO1 or at DCO2, the p-value of the 2nd key secondary endpoint will only be nominal.

The interim analysis (i.e., when the 100th randomised patient has had the opportunity to have their end of Cycle 16 assessment) will take place with approximately 68.5% of the primary endpoint information expected at the primary analysis. For the first family, a split-alpha strategy will be conducted where an alpha of 0.003 (two-sided) will be initially allocated to test at DCO1. If statistical significance is not reached at DCO1, the primary endpoint will be tested again at DCO2 with the remaining alpha of 0.047 (two-sided). If statistical significance of the primary endpoint is reached at DCO1 or DCO2, the overall

alpha of 0.05 (two-sided) will be allocated to the 1st key secondary endpoint. Similarly, if statistical significance of the 1st key secondary endpoint is reached at DCO1 or DCO2, the overall alpha of 0.05 (two-sided) will be allocated to the 2nd key secondary endpoint. For the second and third families, the Haybittle-Peto approach ([Haybittle 1971](#), [Peto et al 1976](#)) will be applied within the family.

[figure not shown]
The expected IF for each key secondary endpoint is 100%. In this case, the overall alpha of 0.05 (two-sided) will be available for DCO1 for the 2nd and 3rd families respectively. Therefore, the alpha split shown in [Figure 2](#) should be considered as a reference example when IF < 100%. The actual IF for each key secondary endpoint will be calculated at the time of the analysis, and adjustments to the alpha will be made accordingly by applying the Haybittle-Peto approach ([Haybittle 1971](#), [Peto et al 1976](#)) within the family.

The testing of the 1st key secondary endpoint will proceed as follows according to the below two scenarios regarding significance on the primary endpoint:

1. If the primary endpoint is not statistically significant at DCO1, then the key secondary variables are not tested at DCO1. If the primary endpoint is statistically significant at DCO2, then the 1st key secondary endpoint will be tested at 0.05 (two-sided), given an expect IF of 100% at DCO1
2. If the primary endpoint is statistically significant at DCO1, then the 1st key secondary endpoint will be tested at 0.05, given an expected IF of 100% at DCO1.

The same approach will be applied to the testing of the 2nd key secondary endpoint based on the significance of the 1st key secondary endpoint, using their corresponding IF and alpha levels.

Figure 2: Multiple Testing Procedure

^a Includes Pain FAS patients who have at least one post-baseline average cycle PAIN-pNF chronic target PN pain intensity score.

^b Includes FAS patients who have a baseline PlexiQOL total score and at least one post-baseline PlexiQOL total score.

^c Significance levels assuming 95.2% and 94.8% information fraction at DCO1 for 1st and 2nd key secondary endpoints, respectively. Final α₂ will be determined at DCO1 based on the actual information fraction using the Haybittle-Peto procedure in EAST. With 100% information fraction at DCO1, α₁ = 0.05.

DCO, data cut-off; FAS, full analysis set; ORR, objective response rate; PAINS-pNF, PAin INTensity Scale for Plexiform Neurofibroma; PlexiQOL, Plexiform Neurofibroma Quality of Life scale; PN, plexiform neurofibroma.

3.3.8 PN Pain Medication Modified WHO Analgesic Ladder and PN Pain Medication Score Changes

The eDiary PN pain medications reported daily by the patient will be assigned by medical review to a drug class and analgesic ladder score identified in [Table 2](#). In case a combination of one or more drug is reported in a daily diary entry, the strongest drug class and its related daily dose will be selected during the medical adjudication process. If all the medications of the combination belong to the same class, precedence will be given to a drug already taken by the patient. Otherwise, the first drug of the combination will be selected.

The strongest drug class and the highest analgesic ladder score at each cycle will be programmatically identified separately for both chronic PN medications and spike PN medications.

Table 2: Modified WHO Analgesic Ladder

Score	Drug class	Examples	
0	No Analgesia		
1	Non-opioids	Acetaminophen, NSAIDs	
2	Neuropathic/ other non-typical pain medications	Pregabalin, Gabapentin, Amitriptyline, Duloxetine Muscle relaxants	Additional class of pain medications added to include typical pain medications used by NF1-PN patients
3	Weak opioids	Codeine	
4	Strong opioids	Morphine	

[figure not shown]
NF1, neurofibromatosis type 1; NSAID, nonsteroidal anti-inflammatory drug; PN, plexiform neurofibroma; WHO, World Health Organisation.

For chronic PN pain medication, changes from baseline will be derived. This definition is used for the derivation of PRO endpoints such as decrease in PN pain medication and chronic target PN pain palliation, as well as the intercurrent event “increase in chronic PN pain medication” of the key secondary PAINS-pNF chronic target PN pain intensity estimand as described in Section 4.2.2.1. No changes from baseline are derived for the spike PN chronic medication.

Following the identification of the strongest drug class in chronic PN pain medication at each cycle, the change in score at each cycle compared to baseline will be programmatically identified following the algorithm outlined in Figure 3. If changes in the strongest drug class from baseline do not follow under the categories of Figure 3. of “Increased” or “Decreased,” the category “No Change” will be assigned. For the cycles where no PN chronic medication has been recorded in the eDiary, the change will be set to “Missing”.

A secondary definition for change from baseline in PN pain medication (Increased/Decreased/No Change) is derived using the investigator analgesic requirement assessment recorded on the e-CRF, indicating whether the reason is PN pain or other pain.

Figure 3: PN Pain Medication Score Changes Algorithm

PN, plexiform neurofibroma; WHO, World Health Organisation.

